6.1. Study Endpoints

Primary Efficacy Endpoints:

[figure not shown]
The primary efficacy endpoint was a clinical response at Week 30 defined as achieving:

[figure not shown]
1. An improvement of at least 1.5 mL/kg/min in pVO₂ as determined by cardiopulmonary exercise testing (CPET) and a reduction of one or more class in NYHA class
OR
2. An improvement of 3.0 mL/kg/min or more in pVO₂ with no worsening in NYHA class.

Secondary Efficacy Endpoints:

- Change from baseline to Week 30 in post-exercise LVOT peak gradient
- Change from baseline to Week 30 in pVO₂ as determined by CPET
- Proportion of subjects who had at least 1 class of NYHA improvement from baseline to Week 30

- Change from baseline to Week 30 in patient-reported health-related QoL as assessed by the Kansas City Cardiomyopathy Questionnaire (KCCQ) clinical summary score (CSS)
- Change from baseline to Week 30 in patient-reported severity of HCM symptoms as assessed by the Hypertrophic Cardiomyopathy Symptom Questionnaire (HCMSQ) shortness-of-breath (SoB) subscore

6.2. Analysis Populations

Four analysis populations are defined in this study:

- Intention-to-treat (ITT) Population: All randomized subjects, regardless of whether they receive study drug, with analyses conducted according to randomized treatment assignment

- Safety Analysis Population: All randomized subjects who receive at least 1 dose of study drug with analyses conducted by actual treatment received.
- PK Analysis Population: All randomized subjects who receive at least 1 dose of mavacamten

6.3. Stratification Factors and Subgroups

[figure not shown]
The baseline values for the following stratification factors will be summarized using descriptive statistics:

- NYHA class (II or III)
- Current treatment with β -blocker (yes or no)
- Type of ergometer (treadmill or exercise bicycle)
- Consent for the CMR substudy (yes or no).

The assigned (IXRS) and actual (CRF) stratification factors will be summarized and listed for mis-stratified participants.

A horizontal bar chart illustrating the percentage of respondents who have heard of various topics. The y-axis lists the topics, and the x-axis represents the percentage, ranging from 0% to 100% in increments of 10%. The bars are black and are set against a white background.

Topic	Percentage
Healthcare	98%
Technology	95%
Finance	92%
Politics	88%
Entertainment	85%
Science	82%
Food	78%
Sports	75%
Business	72%
Art	68%
History	65%
Geography	62%
Mathematics	58%
Chemistry	55%
Physics	52%
Biology	48%
Spanish	45%
French	42%
German	38%
Japanese	35%
Korean	32%
Chinese	28%
Arabic	25%
Swahili	22%
Urdu	18%
Persian	15%
Yoruba	12%
Amharic	8%
Georgian	5%
Ukrainian	3%
Armenian	2%
Malay	1%
Other	1%

6.4. Missing Data

In general, missing data will not be imputed unless specifically stated in this SAP. For mixed-model repeated-measure analyses, missing data are handled implicitly by the model. For the responder analysis of primary and secondary endpoints, refer [Section 8.1](#) and [8.2](#) for the specific handling rules.

Handling of Missing Data:

- For values below the lower limit of quantitation (LLOQ), 1/2 LLOQ will be imputed unless otherwise specified.
- For values above the upper limit of quantitation (ULOQ), ULOQ + 1 unit of significant digit will be imputed unless otherwise specified.
- In general, for missing or partial dates the following is noted:
 - Start Dates:
 - If day is missing, then impute it to be the start of the month (eg, 01 MMM YYYY); except if the month and year is equal to the first dose date month and year then impute the day to be the same day as the first dose date.
 - If month is missing, then impute it to be the start of the year (eg, 01 JAN YYYY), except if the year is equal to the first dose date year then impute the day and month to be the same as the first dose date.
 - If year is missing, then do not impute.
 - End Dates:
 - If day is missing, then impute it to be the end of the month (eg, 31 MMM YYYY), except if the month and year is equal to the last

assessment date month and year then the day should be imputed to the last assessment date day.

- If month is missing, then impute it to be the end of the year (eg, 31DECYYYY), except if the year is equal to the last assessment date year then the day and month should be imputed to the last assessment date day and month.
- If year is missing then do not impute.
- For all other type of dates:
 - If only day is missing, then impute it to be the start of the month (eg, 01MMMYYYY).
 - If month and day are missing, then impute it to be the start of the year (eg, 01JANYYYY).
 - If year is missing, then do not impute.

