Unless otherwise noted, nonsafety (ie. efficacy, pharmacodynamics [PD]) information displayed “by visit” will utilize analysis visits as defined by the analysis visit window as opposed to the visits at which the information was collected (ie, nominal visit). Data collected at unscheduled or early termination (ET) visits will also be mapped to analysis visits. The analysis day for the purposes of deriving the analysis visit windows are derived as follows (reference date is the study drug initiation date, or the randomization date if the study drug initiation date is missing):

- If date of information (year, month, and day) is completely missing, analysis day cannot be calculated and will be treated as missing. If the date is partially missing, date will be imputed according to the rules outlined in [Section 6.4](#).
- If date is < reference date, analysis day = date of information – reference date. If date \geq reference date, analysis day = (date of information – reference date) + 1.

The visit windows for efficacy and PD assessments will be defined according to their respective collection schedules. The rule for defining the analysis window is +/-14 days from the target visit date for all post-baseline visits, except for Week 30 and Week 38, which have +/- 28 day windows. If 2 adjacent visit windows overlap, the limits of the windows will be adjusted to the midpoint between the 2 visits. The specific window definitions for each endpoint are available in Appendix 2 [Table 3 to Table 9](#).

For efficacy and PD analyses, if a value does not fall within an analysis window, it will not be included in the summary analysis. However, these values will be included in data listings and SAS data sets. For post-baseline data, when more than 1 value is available within the same analysis visit, the value collected closest to the target visit day will be used for analysis. If 2 values are the same distance to the closest to target visit day (for example, 1 value is before and the other value is after the target day), then the latest value will be selected as the analysis value. For a specific analysis window, if the latest collected time point has 2 or more values collected, then for continuous data, the average among these results will be derived, and for categorical data (eg, yes or no) the clinically ‘worse’ value will be selected.

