10. SAFETY ANALYSES

All safety analyses will be performed on the Safety Analysis Population using the following common rules:

- The baseline value is defined generally as the last available value before the first administration of study drug.
- The analysis of the safety variables will be descriptive and no hypothesis testing is planned.

The safety analyses will focus on the treatment emergent period, which is defined as the time from the first administration of study drug to the last administration of study drug plus 56 days.

A by-subject listing of all AEs will be provided.

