10.1. Adverse Events

AEs will be mapped to system organ classes (SOCs) and preferred terms (PTs) using the Medical Dictionary for Regulatory Activities (MedDRA) version 21.0. AEs will be monitored during the study, and AE data will be analyzed with respect to overall incidence, as well as severity and relationship of AEs to study drug. AEs with onset during the treatment emergent period or with onset before the first dose of study drug that increase in severity or become serious during the treatment-emergent period will be considered TEAEs.

AE summary tables will present the number and percentage of subjects experiencing at least one TEAE by SOC and PT by treatment group for the Safety Analysis Population. Multiple occurrences of the same event in the same participant will be counted only once in the tables. In addition, the AE summary tables will also be presented by SOC, PT, and severity grade.

AE summary tables will be provided by treatment group for all types of TEAEs: all TEAEs, all treatment-emergent serious AEs, study drug related AEs (per investigator assessment), study drug related SAEs, all TEAEs leading to permanent treatment discontinuation, and all TEAEs leading to death. Similarly, AE incidence during the pre-treatment period (ICF signed date up to the first administration of study drug) will be summarized by SOC and PT. Adverse events of special interest (AESI; per protocol) will be summarized for frequency of occurrence and symptomatic responses.

TEAEs may also be summarized by Standardised MedDRA Queries (SMQs) or other groupings deemed relevant based on AESIs and SAEs observed in the study. Selected TEAEs (e.g. atrial fibrillation, atrial flutter, heart failure, syncope, presyncope and dizziness) will be summarized and listed by historical medical conditions and treatment group. By-subject listings of all AEs, SAEs, TEAEs leading to treatment interruption or discontinuation or study discontinuation will also be provided.

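### SAP 6.4 can give an adverse event that ended before first dose an imputed start on the first dose date, so that it is counted as treatment-emergent

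*SAP*

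**What the plan says.** **Start dates.** SAP Section 6.4 has two special rules. With the day missing and the month and year equal to those of first dose, the instruction is to "impute the day to be the same day as the first dose date". With the month missing and the year equal to that of first dose, it is: "then impute the day and month to be the same as the first dose date". Neither mentions an end date. Imputed end dates, by contrast, are tied to the last assessment date when month and year (or year) match it.

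**Treatment emergence.** SAP Section 10 defines the treatment-emergent period as "the time from the first administration of study drug to the last administration of study drug plus 56 days". SAP Section 10.1 counts as TEAEs "AEs with onset during the treatment emergent period or with onset before the first dose of study drug that increase in severity", or that become serious, in that period. The same section tabulates separately the AEs that arise between consent and first dose.

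**Assessment dates.** For the analysis day, SAP Section 6 states: "If the date is partially missing, date will be imputed according to the rules outlined in" Section 6.4. The category there for dates that are neither start nor end dates reads: "If only day is missing, then impute it to be the start of the month". If the month is missing as well, the date becomes 1 January. Efficacy displays then use the windows of SAP Appendix 2, and "if a value does not fall within an analysis window, it will not be included in the summary analysis".

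**The concern.** Setting an unknown onset to the first dose date is a common convention when the onset could have been on treatment. It fails when the record already shows that the event was over before dosing. The start then falls after the end, and two tables are wrong: one event too many among TEAEs, one too few among pre-treatment AEs.

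The situation can arise in this trial. AEs are collected from consent (Protocol 11.2.1), screening runs up to 35 days, and onset dates depend partly on participant recall.

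The same section is also used to date assessments. Moving a date to the first of the month shifts it back by up to 30 days, and the analysis window then overrides a nominal visit that is known. The values exposed include NYHA class and pVO₂ at Week 30, the two components of the primary endpoint.

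**Working it through.** **1. Adverse events**

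Inputs are the 6.4 start-date rule, the SAP 10 period and the SAP 10.1 TEAE rule. The dates are illustrative.

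- First dose 20 September 2018; recorded start September 2018, day unknown; recorded end 5 September 2018.
- Month and year match first dose, so the imputed start is 20 September 2018.
- Start minus end = 20 − 5 = 15 days, an impossible interval.
- An onset on the first dose date lies in the treatment-emergent period, so the event is a TEAE.
- If only the year 2018 were recorded for the start, the missing-month rule would give the same result.

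With the cap proposed below, the start is no later than 5 September and the event is pre-treatment. With about 110 treated per arm, one such participant changes an incidence by at most 1/110 = 0.9 percentage points, and only if not already counted in that row.

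**2. Week 30 assessments with a missing day**

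Inputs from SAP Appendix 2:

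- NYHA Week 26 covers days 170–197, and Week 30 covers days 198–239.
- CPET has one post-baseline window, days 184–239.
- The Week 30 target is day 211. The ±7-day visit window gives days 204–218.

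For a true analysis day *a* on day of month *m*, the imputed day is *a* − (*m* − 1).

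- NYHA moves to Week 26 when *a* − *m* + 1 ≤ 197. For *a* = 211 that means *m* ≥ 15, or 16/30 = 53% with *m* uniform on 1–30.
- CPET leaves its window when *a* − *m* + 1 ≤ 183. For *a* = 211 that means *m* ≥ 29, or 2/30 = 7%.

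The rules were also applied to every first-dose date in an assumed 2018–2019 calendar:

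| True visit day | NYHA to Week 26 | CPET out of window |
|---|---|---|
| 204 | 77% | 31% |
| 211 | 54% | 8% |
| 218 | 31% | 0% |
| 204–218 together | 54% | 11% |

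Example: with first dose on 1 September 2018, day 211 is 30 March 2019. With the day missing, the date becomes 1 March 2019, which is day 182. NYHA is then a Week 26 value, and CPET, which needs a day above 183, is left out.

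Other on-schedule visits cannot refill the NYHA Week 30 window: Week 26 visits fall on days 183 ± 7 = 176–190 and Week 38 visits on days 267 ± 7 = 260–274. All these percentages are conditional on the day being missing.

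**3. Scale against the planned power**

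SAP Section 5 gives 96% power for 110 per arm, 50% against 25%, two-sided 5%. The pooled normal approximation gives

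Φ[(0.25 − 1.96·√(2·0.375·0.625/110)) / √((0.25 + 0.1875)/110)] = Φ(1.935) = 97.4%,

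and 96.3% with a continuity correction, so the stated figure is reproduced. If, purely as an assumption, 1%, 2% or 5% of responders in both arms were lost, the 97.4% would become 97.1%, 96.9% or 96.2%.

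**The case against.** **On adverse events.** The trigger is narrow. It needs an AE after consent, a partial start date in the month or year of first dose, and a known end before first dose. Protocol 11.2.1 sends pre-dose worsening of existing conditions to medical history, which reduces the pool. The rule over-counts and does not hide events, the safety analysis is descriptive, and every AE is listed by subject. All of this limits the size. It does not rescue the rule, because the end date has already excluded onset on treatment and nothing is gained by ignoring it. For medications the visible text shows no consequence beyond an odd interval.

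**On assessments.** Partial dates should be rare here. CPET data come from digital equipment, NYHA class is recorded at on-site visits, incomplete eCRF data are queried (Protocol 14.2.3), edit checks apply (Protocol 16.1), and Week 30 data are cleaned and locked before the primary analysis (SAP Section 6). This stands, and it makes the efficacy half secondary.

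**A stronger reading.** A reader might infer that a missing day makes a Week 30 participant a non-responder. The documents do not establish that. SAP Section 5 and Protocol 12.4.6.1 do score participants who cannot be assessed as non-responders, but SAP 6.4 refers the handling rules for responder analyses to Sections 8.1 and 8.2, which are not in the public text and may hold a safeguard. Nor does one outcome fit both measures: the move into Week 26 concerns NYHA, while CPET has no Week 26 window and can only drop out.

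**Conclusion.** The adverse-event point holds as a defect in a written rule. For any event with a partial start in the month or year of first dose and a known end before it, SAP 6.4 produces a start after the end and a false TEAE. The rules are introduced as general ones, but no exception for end dates is stated. The number of such events cannot be derived from the documents and is probably small.

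The assessment point holds conditionally. Given a missing day at an on-schedule Week 30 visit, about 54% of NYHA values go to Week 26 and about 7–11% of CPET values leave their window, the range depending on whether the visit is taken at day 211 or spread over days 204–218. The effect on the primary endpoint is unproven and, on the assumed range above, slight. Overall this is a minor correction that is worth making.

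**What to change.** In SAP 6.4, add that an imputed start date may not be later than a known end date, and that an event with an end date before first dose is pre-treatment.

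In SAP Section 6, replace the imputed analysis day for partially dated assessments by two rules:

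- An assessment from a scheduled visit goes to its nominal visit. The SAP already summarizes safety and PK data by nominal visit.
- An unscheduled or early-termination assessment has no nominal week, so its imputed date is bounded by the dates of the adjacent visits.

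Section 8.1 should be checked at the same time, so that the responder rules agree with this. With these rules, none of the on-schedule Week 30 assessments in the calendar check leaves Week 30. The cost is a few sentences and minor programming, with no change to conduct, endpoints or alpha.

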6.5. Multiplicity Control

A sequential testing procedure will be used for multiplicity control. If the primary endpoint is not statistically significantly different between treatment groups, none of the tests for secondary endpoints will be considered statistically significant despite the nominal p-values. Contingent upon significance in the primary endpoint, each of the secondary efficacy endpoints will be tested sequentially in the following order, at a 2-sided alpha level of 0.05:

1. Change from baseline to Week 30 in post-exercise LVOT peak gradient
2. Change from baseline to Week 30 in pVO₂ as determined by CPET
3. Proportion of subjects who had at least 1 class of NYHA improvement from baseline at Week 30
4. Change from baseline to Week 30 in patient-reported health-related QoL as assessed by the KCCQ-23 CSS
5. Change from baseline to Week 30 in patient-reported severity of HCM symptoms as assessed by the HCMSQ SoB subscore

If any of the endpoints are not statistically significantly different between treatment groups, the tests for all subsequent endpoints will not be considered statistically significant despite the nominal p-values.

7. SUBJECT DISPOSITION

The number and percentage of subjects who complete and who prematurely discontinue study drug or study, as well as the reasons for premature discontinuation, will be summarized by randomized treatment assignment for the ITT Population. The reason for screen failure will be summarized for all screened subjects.

7.1. Demographics and Baseline Characteristics

Demographic and baseline characteristics will be summarized descriptively by randomized treatment assignment for the ITT Population.

Body surface area (BSA) will be derived using the Du Bois method.

Cytochrome P450 (CYP) 2C19 genotypes and phenotypes will also be summarized.

7.2. Extent of Study Treatment Exposure and Compliance

The extent of study treatment exposure and compliance will be assessed and summarized by actual treatment received for the Safety Analysis Population.

The duration of study drug exposure is defined as last dose date – first dose date + 1 day, regardless of intermittent interruptions. Adjusted duration will also be derived by taking protocol-defined interruptions into account.

Compliance will be calculated based on the total cumulative dose received divided by the total expected cumulative dose. Compliance of taking pills will be calculated based on the total number of pills taken divided by the adjusted duration.

Treatment exposure and compliance will be summarized using descriptive statistics. The compliance of participants with compliance < 80% and those with compliance > 100% will be summarized.

Actual dose adjustments that occurred during the study and expected dose adjustments based on protocol-specified criteria will be listed by subject and time point. Any inconsistencies will be flagged.

7.3. Protocol Deviations

Prior to Week 38 database lock, all protocol deviations will be reviewed and confirmed by the sponsor. All important protocol deviations will be presented in a by-subject data listing.

Important protocol deviations (IPDs) will be identified by the sponsor and summarized.

International Council for Harmonisation (ICH) E3 guidance defines IPD as a subset of protocol deviations that may significantly impact the completeness, accuracy, and/or reliability of the study data or that may significantly affect a participant's rights, safety, or well-being.

7.4. Medical History and Concomitant Medications

Medical history, HCM history, concomitant and prior medications will be summarized and listed by treatment group for Safety Analysis Population.

[REDACTED]

This figure consists of a grid of horizontal black bars. The bars are of varying lengths, creating a visual representation of data distribution. The grid is composed of approximately 10 columns and 20 rows of bars. Some bars are very short, while others are quite long, extending across multiple grid cells. The overall pattern suggests a high density of data points in certain areas and a sparse distribution in others.

Term	Percentage
GMOs	~10%
Organic	~95%
Natural	~90%
Artificial	~75%
Organic	~95%
Natural	~90%
Artificial	~75%
Organic	~95%
Natural	~90%
Artificial	~75%
Organic	~95%
Natural	~90%
Artificial	~75%
Organic	~95%
Natural	~90%
Artificial	~75%

The figure consists of 20 horizontal black bars of varying lengths, arranged in two main groups. The top group contains 10 bars, and the bottom group contains 10 bars. The bars are set against a white background with no grid lines. The lengths of the bars are as follows:

Group	Bar Number	Approximate Length (Relative)
Top Group	1	Very Long
	2	Very Long
	3	Very Long
	4	Very Long
	5	Very Long
	6	Very Long
	7	Very Long
	8	Very Long
	9	Very Long
	10	Very Long
Bottom Group	1	Medium
	2	Medium
	3	Medium
	4	Medium
	5	Medium
	6	Medium
	7	Medium
	8	Medium
	9	Medium
	10	Medium

10. SAFETY ANALYSES

All safety analyses will be performed on the Safety Analysis Population using the following common rules:

- The baseline value is defined generally as the last available value before the first administration of study drug.
- The analysis of the safety variables will be descriptive and no hypothesis testing is planned.

The safety analyses will focus on the treatment emergent period, which is defined as the time from the first administration of study drug to the last administration of study drug plus 56 days.

A by-subject listing of all AEs will be provided.

10.1. Adverse Events

AEs will be mapped to system organ classes (SOCs) and preferred terms (PTs) using the Medical Dictionary for Regulatory Activities (MedDRA) version 21.0. AEs will be monitored during the study, and AE data will be analyzed with respect to overall incidence, as well as severity and relationship of AEs to study drug. AEs with onset during the treatment emergent period or with onset before the first dose of study drug that increase in severity or become serious during the treatment-emergent period will be considered TEAEs.

AE summary tables will present the number and percentage of subjects experiencing at least one TEAE by SOC and PT by treatment group for the Safety Analysis Population. Multiple occurrences of the same event in the same participant will be counted only once in the tables. In addition, the AE summary tables will also be presented by SOC, PT, and severity grade.

AE summary tables will be provided by treatment group for all types of TEAEs: all TEAEs, all treatment-emergent serious AEs, study drug related AEs (per investigator assessment), study drug related SAEs, all TEAEs leading to permanent treatment discontinuation, and all TEAEs leading to death. Similarly, AE incidence during the pre-treatment period (ICF signed date up to the first administration of study drug) will be summarized by SOC and PT. Adverse events of special interest (AESI; per protocol) will be summarized for frequency of occurrence and symptomatic responses.

TEAEs may also be summarized by Standardised MedDRA Queries (SMQs) or other groupings deemed relevant based on AESIs and SAEs observed in the study. Selected TEAEs (e.g. atrial fibrillation, atrial flutter, heart failure, syncope, presyncope and dizziness) will be summarized and listed by historical medical conditions and treatment group. By-subject listings of all AEs, SAEs, TEAEs leading to treatment interruption or discontinuation or study discontinuation will also be provided.

